4.2.8.2 Analysis of NT-proBNP

NT-proBNP is described in section 3.3.2.1. NT-proBNP is assumed to be log-normally distributed. Baseline and post-baseline definitions are detailed in section 3.1.2. Tables and listings will be based on the ITT population and presented for each treatment group.

An overview of the MMRM analysis (section 4.1.2) performed to compare MEDI6570 CCI versus placebo, MEDI6570 CCI versus placebo, MEDI6570 CCI versus placebo and pooled MEDI6570 CCI versus placebo will be presented. This overview will include the results from the 4 comparisons of the MMRM fit on NT-proBNP variable (section 3.3.2.1).

NT-proBNP will be summarized descriptively as continuous variable at baseline, Days 29, 85, 113, 122, 225 and 253 for observed value and change from baseline. Change of NT-proBNP will be also presented in figure with mean and SD by visit.

A MMRM model as described in section 4.1.2 for change of NT-proBNP, at Day 253 will be also presented. A forest plot will also be presented in figure for the 4 comparisons between active groups and placebo using the MMRM model for change of NT-proBNP at Day 253.

NT-proBNP will be also reported in a listing for the ITT population.

These summaries (tables and figures) will be also repeated for final analysis only among subjects with reduced ejection fraction (defined as $<50\%$ at baseline).

4.2.8.2.1 Sensitivity analysis of NT-proBNP

A sensitivity analysis with the same MMRM model will be performed on the ITT population but without subjects having received both CCI and CCI (sensitivity analysis 1).

A second sensitivity analysis may be performed by including all analysis visits regardless of protocol version.

4.2.8.2.2 Subgroup Analysis of NT-proBNP

Subgroup analysis will present the same summary and inferential tables (MMRM model described in section 4.1.2) for the ITT population described in the previous section (excluding sensitivity analysis). A complete list of the subgroup analyses at final analysis is provided below.

The following subgroups at the final analysis will be analysed:

- Sex (*Male; Female*)
- Age (<65 ; ≥ 65 years)
- Race (*Caucasian; Non-Caucasian*)
with *Caucasian* = White and *Non-Caucasian* = American Indian or Alaska Native, Asian, Black or African American, Native Hawaiian or Other Pacific Islander, Other.
- Geographic region
 - *Asia, North America; Rest of the World Western (North America and Rest of the World); Asia*
Asia will not be repeated in the second subgroup.
- Diabetes mellitus (*Presence; Absence*)
with *Presence* = if diabetes mellitus (type 1 or type 2) in Medical History (MH) or Cardiac History and Risk Factor (SPECHIS) forms and *Absence* otherwise.
- Smoking Status (*Smoker; Non-smoker*)
with *Smoker* = current or former smoker and *Non-smoker* = never smoked.
- Qualifying MI Type (*STEMI; NSTEMI*)
using Indication field from Coronary Revascularisation - Qualifying Event (PROCCA) form
- Baseline eGFR (<60 mL/min/1.73 m 2 ; ≥ 60 mL/min/1.73 m 2)
- Baseline NT-ProBNP
 - ($< \text{Median}$; $\geq \text{Median}$)
 - (< 125 pg/mL; ≥ 125 pg/mL)

- **CCI**
[REDACTED]

■ CCI [REDACTED]

- Baseline LVEF (<50%; >=50%)

4.2.8.3 Echocardiogram analysis

As described in section 3.3.2.2, the variables assessed by echocardiography include:

- LVEF
- GLS

LVEF and GLS, as part of the echocardiography evaluations, are assumed to be normally distributed.

Baseline and post-baseline definitions are detailed in section 3.1.2. Tables, listings and figures will be based on the Echocardiogram analysis population and presented for each treatment group.

An overview of the ANCOVA analysis (section 4.1.1) performed to compare MEDI6570 CCI [REDACTED] versus placebo, MEDI6570 CCI [REDACTED] versus placebo, MEDI6570 CCI [REDACTED] versus placebo and pooled MEDI6570 CCI [REDACTED] versus placebo will be presented. This overview will include the results from the 4 comparisons of the change from baseline to Day 253 of LVEF and of GLS. The same ANCOVA analysis will be done for this overview to present results for subjects with reduced ejection fraction (<50% at baseline).

LVEF and of GLS will be summarized descriptively as continuous variable at Baseline and Day 253 for observed value, change and percent change from baseline.

An ANCOVA model as described in section 4.1.1 for change from baseline in LVEF and for change from baseline in GLS, respectively at Day 253 will be presented. Forest plots will also be presented in separate figures for the 4 comparisons between active groups and placebo using the ANCOVA model for change of LVEF and change of GLS, at Day 253.

LVEF and GLS will be also reported in a listing for the Echocardiogram analysis population.

These summaries (tables and figures) will be also repeated for both variables among subjects with reduced ejection fraction (defined as <50% at baseline).

4.2.8.3.1 Sensitivity analysis of Echocardiogram variables

A sensitivity analysis will be performed for LVEF with the same ANCOVA model on the Echocardiogram analysis population but without subjects having received both CCI and CCI (sensitivity analysis 1).

4.2.8.3.2 Subgroup Analysis of Echocardiogram variables

Subgroup analysis will present both summary and inferential tables (ANCOVA model described in section 4.1.1) described in the previous section for the Echocardiogram analysis population (excluding sensitivity analysis). A complete list of the subgroup analyses at final analysis is provided below.

The following subgroups at the final analysis will be analysed:

- Sex (*Male; Female*)
- Age (<65 ; ≥ 65 years)
- Race (*Caucasian; Non-Caucasian*)
 - with *Caucasian* = White and *Non-Caucasian* = American Indian or Alaska Native, Asian, Black or African American, Native Hawaiian or Other Pacific Islander, Other.
- Geographic region
 - *Asia, North America; Rest of the World*
 - *Western (North America and Rest of the World); Asia*
Asia will not be repeated in the second subgroup.
- Diabetes mellitus (*Presence; Absence*)
 - with *Presence* = if diabetes mellitus (type 1 or type 2) in Medical History (MH) or Cardiac History and Risk Factor (SPECHIS) forms and *Absence* otherwise.
- *Smoking status (Smoker; Non-Smoker)*
 - with *Smoker* = current or former smoker and *Non-smoker* = never smoked.
- Qualifying MI Type (*STEMI; NSTEMI*)
 - using Indication field from Coronary Revascularisation - Qualifying Event (PROCCA) form
- Baseline eGFR ($<60 \text{ mL/min/1.73 m}^2$; $\geq 60 \text{ mL/min/1.73 m}^2$)
- Baseline NT-ProBNP
 - ($< \text{Median}$; $\geq \text{Median}$)
 - ($< 125 \text{ pg/mL}$; $\geq 125 \text{ pg/mL}$)
- **CCI**
[REDACTED]

- CCI
[REDACTED]
- Baseline LVEF (<50%; >=50%)

4.2.9 Other secondary endpoints

Other secondary endpoints include:

- Immunogenicity (ADA incidence and Titre)
- Pharmacokinetic concentrations

4.2.9.1 Immunogenicity analysis

The endpoints to evaluate immunogenicity of MEDI6570 are ADA incidence and Titre. ADA and Titre are described in section 3.3.3.1. Baseline and post-baseline definitions are detailed in section 3.1.2. Tables and listings will be based on the Immunogenicity population and presented for each treatment group and overall (total will not include placebo subjects).

ADA will be summarised in IDMC reports (if data available prior to the meeting) and at final analysis using the following categories:

- ADA negative at all assessments, including baseline and post-baseline (ADA negative)
- ADA positive at baseline and/or post-baseline (ADA prevalence)
- TE-ADA positive (ADA incidence)
- Treatment-induced ADA positive
- Treatment-boosted ADA positive
- TE-ADA negative
- Both baseline and post-baseline positive
- Only baseline positive
- ADA persistently positive
- ADA transiently positive
- TE-ADA positive with maximum titre > median of maximum titres.

ADA negative is defined as having ADA negative at all assessment, including baseline and post-baseline. TE-ADA positive is defined as the sum of treatment-induced ADA positive (ADA negative at baseline and post-baseline ADA positive) and treatment-boosted ADA positive (ADA positive at baseline and boosted the pre-existing titre during the study period).

TE-ADA negative is defined as ADA positive but not fulfilling the definition of TE-ADA positive. ADA incidence is the proportion of TE-ADA positive subjects in a population.

ADA persistently positive is defined as ADA negative at baseline and ADA positive at ≥ 2 post-baseline assessments (with ≥ 16 weeks between first and last positive) or ADA positive at last post-baseline assessment. ADA transiently positive is defined as ADA negative at baseline, having at least one post-baseline ADA positive assessment and not fulfilling the conditions of ADA persistently positive.

The median of maximum titres is calculated based on the maximum titre for each ADA positive subject within each treatment group (including both baseline and post-baseline measurements).

ADA will be also reported in a listing in IDMC reports (if data available prior to the meeting) and at final analysis.

ADA will be summarized by visit at final analysis only as categorical variable with the number and percentages with a positive result at the baseline, Days 10 to 141, Day 225, Day 253 and Day 325/405. Immunogenicity titre will be summarized descriptively as continuous variable, only for ADA positive tests, with median, interquartile range, minimum and maximum, at same analysis visits as ADA.

ADA positive subjects will also be listed at final analysis only.

All ADA analyses above except the summary statistics by visit will include scheduled and unscheduled ADA measurements.

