9.4.2.2 Secondary Endpoints

NT-proBNP

Secondary endpoint of relative change from baseline in NT-proBNP will be analyzed based on the ITT population. Relative change from baseline is defined as the ratio of the post-baseline visit value over the baseline value, expressed as a percentage. A MMRM analysis will be performed. The dependent variable is change from baseline for the log-transformed value of NT-proBNP, ie $\log(\text{post-baseline visit value}) - \log(\text{baseline value})$. The results will be back-transformed to the original scale. The model will include fixed effects of treatment group, visit, treatment group-by-visit interaction, and randomization strata, with baseline

NT-proBNP as a covariate. Repeated measures for the model will be visit within subjects. An unstructured covariance structure will be used for the repeated measures. In case the model does not converge, back-up covariance structures and other analysis solutions will be detailed in the SAP.

Secondary Endpoints Derived from Echocardiogram and CTA

Secondary endpoints that are measured by echocardiogram or CTA will be analyzed based on the Echocardiogram or CTA Analysis Population, respectively. ANCOVA analyses similar to the primary endpoint will be performed; the model will adjust for treatment group, respective baseline value, and randomization strata.

Immunogenicity Analyses

The Immunogenicity Population will be used for the immunogenicity analyses.

The number and percentage of participants with confirmed positive serum ADA to MEDI6570 will be reported by dose level. Titer data will be summarized descriptively.

The potential impact of ADA on MEDI6570 PK, efficacy, and safety will be evaluated as data allow.

PK Analyses

The PK Population will be used for the PK analyses.

MEDI6570 serum concentration data will be summarized descriptively, tabulated and plotted.

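### The high-titre ADA row takes its cut-off from each treatment group's own median, so it cannot show a dose difference in titre level

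*SAP*

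**What the plan says.** SAP 4.2.9.1 lists eleven ADA categories. The last is "TE-ADA positive with maximum titre > median of maximum titres". The cut-off is then defined: "The median of maximum titres is calculated based on the maximum titre for each ADA positive subject within each treatment group". Samples taken before the first dose count towards a participant's maximum, as do later ones.

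The set that fixes the median is wider than the set that can be marked. The median uses every ADA-positive participant, but only TE-ADA positives can enter the category, and "TE-ADA negative is defined as ADA positive but not fulfilling the definition of TE-ADA positive".

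The tables use the Immunogenicity population, with a column per treatment group and an overall column that leaves placebo out. The SAP does not say which median applies in the overall column. The categories go into IDMC reports when data are available, and into the final analysis.

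Titre also appears elsewhere in the same section: "Immunogenicity titre will be summarized descriptively as continuous variable, only for ADA positive tests, with median, interquartile range, minimum and maximum". That summary is by visit and at final analysis only. Protocol 9.4.2.2 says that "The number and percentage of participants with confirmed positive serum ADA to MEDI6570 will be reported by dose level" and asks for a descriptive summary of titre.

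**The concern.** A row that counts high-titre participants by dose invites the reader to compare doses. Here the yardstick moves with the titres that it is meant to classify: a dose that induces much higher titres also gets a much higher cut-off. The same titre can count as high in one group and not in another, and barely detectable titres can count as high in the placebo column.

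Titre is named with ADA incidence under the immunogenicity objective, and the protocol describes the study as dose-range finding. At stake is a descriptive table that can mislead, in the final report and in IDMC reports. No hypothesis test or decision rule depends on it.

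**Working it through.** The documents state no figure for this row, so there is nothing to reproduce. They also give no titres, dilution scheme or ADA rate. Steps 1 and 2 need no assumption. The numbers in steps 3 to 7 are illustrations. The 123 is the number planned per continuing active dose in Protocol 4.1, used as a stand-in for the Immunogenicity population.

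1. **Ceiling.** Among n values, at most floor(n/2) lie strictly above their own median. In 20,000 simulated titre sets, with and without ties, the marked share never exceeded 0.50.

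2. **Insensitivity to level.** If every titre t in a group is multiplied by c > 0, the median m becomes cm, and ct > cm exactly when t > m. The same participants are marked.

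3. **Small example, all TE-ADA positive.**
   - Group A: 10, 20, 40, 80. Own median (20 + 40)/2 = 30; 2 of 4 marked.
   - Group B: 640, 1280, 2560, 5120. Own median (1280 + 2560)/2 = 1920; 2 of 4 marked.
   - Common median (80 + 640)/2 = 360; 0 of 4 and 4 of 4 marked.

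4. **Larger example.** 30 ADA-positives in each of two groups, titres 16-fold higher in one.
   - Own medians: 15 and 15.
   - Common median: 3 and 27, or 3/123 = 2.4% and 27/123 = 22.0%.

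5. **Incidence moves the row.** Same titre distribution, 12 and 49 ADA-positives of 123. The rule marks floor(12/2) = 6 and floor(49/2) = 24, or 4.9% and 19.5% of 123. The gap reflects incidence alone.

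6. **The TE mix moves the row.** Take 20 ADA-positives, ten with titre 10 and ten with titres from 100 to 1000, so the median is (10 + 100)/2 = 55. If the ten TE-ADA positives hold the higher titres, 10 of 10 are marked. If they hold the lower, 0 of 10 are.

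7. **Ties can reverse the row, and the overall column is ambiguous.**
   - Group C: 20 titres of 10 and 10 of 20. Median 10; 10 of 30 marked.
   - Group D: 10 titres of 10 and 20 of 20. Median 20; 0 of 30 marked, although D has more high titres.
   - Common median of the 60 values (30 tens, 30 twenties): 15. It marks 10 of 30 and 20 of 30, in the right order.
   - Overall column: adding the group counts gives 10 + 0 = 10 of 60. A median computed for the pooled column gives 30 of 60. The SAP allows either reading.

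**The case against.** A reader might infer that the row is fixed by construction, or that it cannot show any dose difference. The documents do not support that. Half is a ceiling, not a fixed value, and the tables are based on the Immunogenicity population, so the row moves with incidence, TE mix and ties (steps 5 to 7). What the row cannot show is a difference in titre level.

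A reader might also infer that the trial has no other comparison of titre between doses. It has one. The by-visit titre summary falls under the section's rule that tables are presented for each treatment group, and it would reveal the contrast in step 3. This point stands and is the main reason why the impact is limited. The by-visit summary is only a partial substitute, however:
- It leaves out unscheduled samples, which the categories include.
- It describes positive tests at each visit, not each participant's maximum.
- Its visits go from Day 141 to Day 225. Day 169 is not listed, although SAP 3.3.3.1 names it and Protocol Amendment 2 moved an ADA sample to it.
- It is not specified for IDMC reports.

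It would go too far to say that the IDMC sees titre only through this row. It also receives an ADA listing, whose columns the SAP does not specify, and Protocol Appendix A 5 lets it merge treatment codes with study data.

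The last objection concerns the remedy. SAP 4.2.9.2 plots PK by ADA category and SAP 4.2.10.7 tabulates AEs by ADA category. If the high-titre category feeds those displays, a common cut-off could confound titre class with dose; in step 3 it puts nobody from A and everyone from B in the high class. The documents do not tie this category to those displays, but the caution is fair and the fix below allows for it.

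**Conclusion.** The point holds for titre level. As written, the row marks at most half of each group's ADA-positives and does not respond to a shift in a group's titres. The differences that it can show come from incidence, TE mix and ties, and could be read as titre differences under a high-titre label. The cut-off for the overall active column is undefined.

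The consequence is limited and descriptive: the secondary endpoint of titre does not rest on this row, and no efficacy analysis is touched. The ceiling and the insensitivity follow from the definition. The example counts rest on assumed titres and ADA rates and show only how large the distortion could be.

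**What to change.** In SAP 4.2.9.1, for this table, replace *within each treatment group* with *across all ADA positive subjects in the MEDI6570 groups combined*. Apply that single cut-off in every column, including overall and placebo. Print its value in the footnote together with each group's own median.

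If the high-titre category is also used in the PK or AE displays by ADA category, show those within dose group; the group's own median may be kept there.

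The cost is one phrase in the SAP, a small programming change and a footnote, with no new data. The small downside is that a common cut-off may leave few or no high-titre participants in some groups.

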4.2.9.2 PK analysis

Tables and figures will be based on the PK population and presented for each treatment group at final analysis.

Individual serum concentrations ($\mu\text{g/mL}$) of MEDI6570 will be summarized descriptively as a continuous variable by analysis visit for each treatment group and tabulated. Descriptive statistics include, but not limited to, geometric mean (GeoMean), geometric coefficient of variation (GeoCV), arithmetic mean, SD, geometric SD (GeoSD), minimum, median, maximum, n and n below the lower limit of quantification (LLOQ). The LLOQ for MEDI6570 is 0.03280 $\mu\text{g/mL}$.

GeoMean and GeoSD of serum concentrations ($\mu\text{g/mL}$) of MEDI6570 vs analysis visit and treatment group will be presented in graph using log-linear and linear scale.

Individual serum concentrations ($\mu\text{g}/\text{mL}$) of MEDI6570 vs actual time will be plotted by treatment group using log-linear and linear scale.

Individual serum concentrations ($\mu\text{g}/\text{mL}$) of MEDI6570 for each actual time point will be listed.

If data allows, impact of ADA on PK will be evaluated by plotting serum concentrations ($\mu\text{g}/\text{mL}$) time profile of MEDI6570 by ADA category using box plot and by plotting individual serum concentrations ($\mu\text{g}/\text{mL}$) time profile of MEDI6570 by ADA category using spaghetti plot.

4.2.9.2.1 Handling of concentrations below Lower Limit of Quantification (LLOQ)

Individual concentrations below the LLOQ of the bioanalytical assay will be reported as NQ (Not Quantifiable) in the listings with the LLOQ defined in the footnotes of the relevant TFLs. Individual concentrations that are Not Reportable will be reported as NR and those that are missing will be reported as NS (No Sample) in the listings.

Concentrations that are NQ, NR or NS will be handled as follows for the provision of descriptive statistics:

- Any values reported as NR or NS will be excluded from the summary tables and corresponding figures.
- At a time point where less than or equal to 50% of the concentration values are NQ, all NQ values will be set to the LLOQ, and all descriptive statistics will be calculated accordingly.
- At a time point where more than 50% (but not all) of the values are NQ, the GeoMean, the GeoSD, GeoMean \pm GeoSD and GeoCV% will be set to Not Calculable (NC). The maximum value will be reported from the individual data, and the minimum and median will be set to NQ.
- If all concentrations are NQ at a time point, no descriptive statistics will be calculated for that time point. The GeoMean, minimum, median and maximum will be reported as NQ and the GeoCV%, GeoSD and GeoMean \pm GeoSD as NC.
- The number of values below LLOQ ($n < \text{LLOQ}$) will be reported for each time point together with the total number of collected values (n).
- Three observations $> \text{LLOQ}$ are required as a minimum for a serum concentration to be summarized. Two observations $> \text{LLOQ}$ are presented as minimum and maximum with the other summary statistics as NC. One observation $> \text{LLOQ}$ is presented as maximum with the other summary statistics as NC.

4.2.10 Exploratory efficacy endpoints

4.2.10.1 CCI

[REDACTED]

[REDACTED]

[REDACTED]

[REDACTED]

[REDACTED]

[REDACTED]

CCI

[REDACTED]

[figure not shown]
[figure not shown]
[REDACTED]

4.2.10.1.1 CCI

- CCI
[REDACTED]
- [REDACTED]
- [REDACTED]
- [REDACTED]
- 4.2.10.2 CCI
[REDACTED]
- 4.2.10.3 CCI
[REDACTED]
- [REDACTED]
- [REDACTED]
- [REDACTED]

CCI

4.2.10.4 CCI

4.2.10.5 CCI

[REDACTED]

[REDACTED]

[REDACTED]

[REDACTED]

[REDACTED]

[REDACTED]

[REDACTED]

[REDACTED]

4.2.10.6 CCI

[REDACTED]

4.2.10.7 Adverse events

After having assigned the AEs to the corresponding analysis phase as described in section [3.3.5.1](#), the AEs will be summarized for each treatment group and overall (total will not include placebo subjects). The AEs tables will be based on the as-treated population except the AE by ADA tables which will be based on the Immunogenicity population. Summary tables will include AEs in the on-treatment phase and AEs in the follow-up phase.

Summary tables are listed below.

An overview table containing:

- Number and percentage of subjects with any AEs
- Number and percentage of subjects with any AEs with outcome of death
- Number and percentage of subjects with any SAE (including events with outcome = death)
- Number and percentage of subjects with any AEs leading to discontinuation of treatment
- Number and percentage of subjects with any AEs leading to withdrawal from study

Subjects with multiple events in the same category are counted only once in that category.
Subjects with events in more than 1 category are counted once in each of those categories.

An overview table containing:

- Any AE
- Any AEs with outcome of death
- Any SAE (including events with outcome of death)
- Any AE leading to discontinuation of treatment
- Any AE leading to withdrawal from study

Multiple events in the same category are counted multiple times in that category. Multiple events belonging to more than 1 category are counted multiple times in each of those categories.

The following summary tables will be presented by SOC and PT:

- The number and percentage of subjects with any AEs
- The number of AEs
- The number and percentage of subjects with AEs with outcome of death
- The number of SAEs
- The number and percentage of subjects with SAEs
- The number and percentage of subjects with SAEs, assessed by investigator as possibly related to investigational product
- The number and percentage of subjects with AEs leading to discontinuation
- The number and percentage of subjects with any bleedings (all events from bleeding event form or from adverse event form with SMQ= “Haemorrhages narrow”)
- The number and percentage of subjects with any injection site reactions (all events from ISR form or from adverse event form with HLT= “Injection site reactions”)
- Overall summary of number and percentage of subjects with any AEs by ADA (anti-drug antibody category)
- The number and percentage of subjects by ADA (anti-drug antibody category)

The following summary tables will be presented by PT:

- The number and percentage of subjects with most common AEs (frequency of >5%). Most common should be defined according to % in any of the treatment groups.
- The number and percentage of subjects with any AEs by maximum reported intensity.
- The number and percentage of subjects with any AEs and investigator's causality assessment. If a subject has multiple events in the same PT, the event with the strongest relationship will be counted.

Where number of subjects with AEs are summarized by system organ class (SOC) and/or preferred term (PT), subjects with multiple events in the same SOC/PT are counted only once in that SOC/PT. Subjects with events in more than one SOC/PT are counted once in each of those SOCs/PTs.

Additionally, the following tables will be presented:

- The number and percentage of subjects with non-serious AEs occurring with a frequency > 5.0% in any treatment group for each SOC and PT.

This table will be produced as a separate pdf output to meet clinical trial transparency requirements and not for inclusion in the clinical study report (CSR). It will be delivered at the same time as the CSR outputs.

Key subject information for subjects with:

- AEs with outcome of death
- SAEs
- AEs leading to discontinuation of study treatment

The durations reported in these tables, will be derived only for fully completed dates as below:

- Time from first dose of treatment to AE (in days) will be calculated as the AE start date minus date of first dose +1.
- Time from first dose to death (in days) will be calculated as the date of death minus date of first dose +1.
- The same approach will be used for deriving time from start of treatment to AE becoming serious or discontinuation.
- Time from last dose prior to AE start and last dose prior to death will be calculated as the date of death minus the date of last dose prior to AE/death +1.

A listing will be provided for all the AEs regardless of the analysis phases for all subjects included in the as-treated population.

All analyses will be conducted in IDMC reports and at final analysis.

